Appendix 6. AIDS-Defining Conditions (CDC Guidelines) {Selik et al 2014}

- Bacterial infections, multiple or recurrent*
- Candidiasis of bronchi, trachea, or lungs
- Candidiasis of esophagus
- Cervical cancer, invasive[†]
- Coccidioidomycosis, disseminated or extrapulmonary
- Cryptococcosis, extrapulmonary
- Cryptosporidiosis, chronic intestinal (> 1 month's duration)
- Cytomegalovirus disease (other than liver, spleen, or nodes), onset at age > 1 month
- Cytomegalovirus retinitis (with loss of vision)
- Encephalopathy attributed to HIV[§]
- Herpes simplex: chronic ulcers (> 1 month's duration) or bronchitis, pneumonitis, or esophagitis (onset at age > 1 month)
- Histoplasmosis, disseminated or extrapulmonary
- Isosporiasis, chronic intestinal (> 1 month's duration)
- Kaposi sarcoma
- Lymphoma, Burkitt (or equivalent term)
- Lymphoma, immunoblastic (or equivalent term)
- Lymphoma, primary, of brain
- *Mycobacterium avium* complex or *Mycobacterium kansasii*, disseminated or extrapulmonary
- *Mycobacterium tuberculosis* of any site, pulmonary[†], disseminated, or extrapulmonary
- Mycobacterium, other species or unidentified species, disseminated or extrapulmonary
- *Pneumocystis jirovecii* (previously known as "*Pneumocystis carinii*") pneumonia
- Pneumonia, recurrent[†]

- Progressive multifocal leukoencephalopathy
- *Salmonella* septicemia, recurrent
- Toxoplasmosis of brain, onset at age > 1 month
- Wasting syndrome attributed to HIV[§]

* Only among children aged < 6 years

† Only among adults, adolescents, and children aged ≥ 6 years

§ Suggested diagnostic criteria for these illnesses, which might be particularly important for HIV encephalopathy and HIV wasting syndrome, are described in the following references {[Centers for Disease Control and Prevention 1994](#)}, {[Centers for Disease Control and Prevention 1992](#)}.

## LIST OF ABBREVIATIONS

3TC	lamivudine
ABC	abacavir
AE	adverse event
ALT	alanine aminotransferase
ARV	antiretroviral
AST	aspartate aminotransferase
BMI	body mass index
CI	confidence interval
CK	creatinine kinase
CRF	case report form
CSR	clinical study report
DMC	data monitoring committee
ECG	electrocardiogram
ESDD	early study drug discontinuation
ET	early termination
FAS	Full Analysis Set
FACIT	Functional Assessment of Chronic Illness Therapy
FDA	Food and Drug Administration
FDC	fixed dose combination
GFR	glomerular filtration rate
Gilead	Gilead Sciences
Hb	hemoglobin
HIVTSQ	HIV Treatment Satisfaction Questionnaire
HLGT	high level group term
HLT	high-level term
ICH	International Conference on Harmonization (of Technical Requirements for Registration of Pharmaceuticals for Human Use)
ID	identification
iDMC	Internal Data Monitoring Committee
INSTI	integrase strand transfer inhibitor
ITT	intent to treat
KM	Kaplan-Meier
LOQ	limit of quantitation
MedDRA	Medical Dictionary for Regulatory Activities
NNRTI	non-nucleoside reverse transcriptase inhibitors
NRTI	nucleoside reverse transcriptase inhibitors
PI	protease inhibitor
PP	per protocol
PRO	patient reported outcomes

PT	preferred term
PVF	pure virologic failure
PVR	pure virologic response
Q1, Q3	first quartile, third quartile
SAE	serious adverse events
SAP	statistical analysis plan
SD	standard deviation
SI (units)	international system of units
SOC	system organ class
TAM	thymidine analogue associated mutations
TEAE	treatment-emergent adverse event
TFLs	tables, figures, and listings
UACR	urine albumin to creatinine ratio
UPCR	urine protein to creatinine ratio
ULN	upper limit of normal
VAS	visual analogue scale
WHO	World Health Organization

## 1. INTRODUCTION

This statistical analysis plan (SAP) describes the statistical analysis methods and data presentations to be used in tables, figures, and listings (TFLs) in the clinical study report (CSR) for Study GS-US-292-1824. This SAP is based on the study protocol (Amendment 1) dated 19 August 2016 and the electronic case report form (eCRF). The SAP will be finalized before database finalization. Any changes made after the finalization of the SAP will be documented in the CSR.

### 1.1. Study Objectives

The primary objective of this study is as follows:

- To evaluate the efficacy of elvitegravir/cobicistat/emtricitabine/tenofovir alafenamide (E/C/F/TAF) fixed dose combination (FDC) after switching from a stable regimen consisting of emtricitabine (FTC)/tenofovir disoproxil fumarate (TDF) or abacavir (ABC)/lamivudine (3TC) plus a third antiretroviral agent in maintaining HIV-1 RNA < 50 copies/mL at Week 12 (using pure virologic response) in subjects harboring the archived nucleoside/nucleotide reverse transcriptase inhibitor (NRTI) resistance mutation M184V and/or M184I in HIV-1 reverse transcriptase

The secondary objectives of this study are as follows:

- To determine the safety and tolerability of E/C/F/TAF FDC in subjects switching from 2 NRTI plus third antiretroviral agent regimens
- To evaluate the development of new resistance mutations in subjects who develop virologic failure after switching to E/C/F/TAF FDC
- To determine the durability of efficacy at Weeks 24 and 48 in maintaining HIV-1 RNA < 50 copies/mL using pure virologic response (PVR)

### 1.2. Study Design

This is an open-label, single arm, multicenter, two part study to evaluate the efficacy and safety of switching to E/C/F/TAF FDC in HIV-1 infected adult subjects who are virologically suppressed (HIV-1 RNA < 50 copies/mL) harboring an archived isolated M184V and/or M184I mutation and who have been on a stable regimen consisting of FTC/TDF or ABC/3TC plus a third antiretroviral agent for  $\geq 6$  consecutive months prior to screening. Eligible subjects will be assigned to E/C/F/TAF FDC.

Enrollment of subjects will proceed in 2 parts: Part 1 and Part 2. Each part will consist of subjects who have a documented presence of M184V and/or M184I mutations (mixtures are acceptable) in reverse transcriptase.

In Part 1, the subjects will have M184V and/or M184I (mixtures are acceptable) in reverse transcriptase WITHOUT any other NRTI resistance mutation (including thymidine analogue-associated mutations (TAMs) [TAMs are: M41L, D67N, K70R, L210W, T215Y/F, and K219Q/E/N/R], K65R, K70E, T69 insertion, and/or Q151M mutation complex [A62V, V75I, F77L, F116Y, Q151M]. If the rate of virologic failure in Part 1 is deemed acceptable, after the internal Data Monitoring Committee (iDMC) officially completes the interim review, the study will continue to Part 2 (with the expanded entry criteria).

In Part 2, the subjects will have M184V and/or M184I (mixtures are acceptable) in reverse transcriptase WITH or WITHOUT 1 or 2 TAMs. Evidence of K65R, K70E, T69 insertion, and/or Q151M mutation complex in subjects in addition to the resistance mutations above will not be eligible for entry into the study.

The study will consist of a 42-day screening period (within 42 days before Day 1 visit), followed by a 48 week treatment period. After Day 1, subjects will return for study visits at Weeks 4, 8, 12, 16, 24, 36 and 48. End of study is defined as completion of the 48 weeks of treatment and the 30 Day Follow-Up visit.

Plasma HIV-1 RNA, assessment of adverse events (AEs) and concomitant medications are performed at screening, baseline, Week 4, Week 8, Week 12, Week 16, Week 24, Week 36, and Week 48/Early Study Drug Discontinuation (ESDD) visit.

Laboratory analyses (CD4+ cell count, estimated glomerular filtration rate [eGFRCG], serum chemistry, hematology, urinalysis and urine chemistry, pregnancy testing [for females of childbearing potential]), and vital signs are performed at screening, baseline, Week 4, Week 8, Week 12, Week 24, Week 36, and Week 48/ESDD visit. Metabolic assessments are performed at baseline, Week 24, and Week 48.

12-Lead electrocardiogram (ECG) (performed supine) is collected at screening and Week 48/ESDD only.

Hepatitis B virus (HBV) and hepatitis C virus (HCV) serologies (ie, HBV virus surface antigen [HBsAg], hepatitis B core antibody [HBcAb], and hepatitis C virus [HCVAb] serologies [reflex HCV RNA is performed in subjects with positive HCVAb serology]) are performed at screening only. Height is collected at screening only.

For further details of assessments taken at each visit, see Schedule of Assessments, [Appendix 1](#).

### **1.3. Sample Size and Power**

The primary analysis will describe the point estimate and 95% confidence interval (CI) around the proportion of subjects with HIV-1 RNA < 50 copies/ mL for the primary endpoint. If the observed pure virologic response rate is 90%, then with 100 participants, the width of the 95% CI will be ± 5.9% (large sample size approximation and binomial distribution).

After the Week 12 (iDMC review for Part 1, the actual pure virologic response rate in Part 1 was determined to be 100%. Based on this, it was reasonable to assume that the observed pure virologic response rate for the study will be 95% or higher, and the sample size of the study was reduced to 64 subjects. Under this assumption, with a sample size of 64 subjects, the width of the 95% CI will be  $\pm 5.3\%$  or lower (large sample size approximation and binomial distribution).

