8.4. Efficacy Analysis

8.4.1. Primary Analysis

The primary endpoint of pure virologic response (PVR) with HIV-1 RNA < 50 copies/mL at Week 12 will be computed.

The following criteria are considered for classifying subjects as a pure virologic responder at Week 12:

- Subject remains on study treatment
- No confirmed rebound as defined by:
 - HIV-1 RNA \geq 50 copies/mL on 2 consecutive visits;
 - HIV RNA \geq 50 copies/mL during study followed by premature discontinuation of study

Note: For confirmation of viral rebound, the first HIV-1 RNA must occur on or before the upper limit of the Week 12 analysis window, the confirming event (i.e., the second of the consecutive HIV-1 RNAs or premature study discontinuation) can occur after the upper limit of the Week 12 analysis window.

Subjects who meet the above criteria are pure virologic responders at Week 12; otherwise subjects are pure virologic failures (PVF) at Week 12. The 95% CI will be computed using normal approximation to the binomial proportions of PVR

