#### 6.1.2. Statistical Hypothesis for the Primary Efficacy Endpoint

No formal statistical hypotheses are being tested.

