#### 6.1.3. Primary Analysis of the Primary Efficacy Endpoint

The number and proportion of subjects with PVR and PVF at Week 12 will be summarized overall and by Parts 1 and 2. Two-sided 95% CIs will be constructed for the overall estimate of PVR and PVF using the normal approximation and the exact method.

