#### **6.2.2. Analysis Methods for Secondary Efficacy Endpoints**

##### **6.2.2.1. Analysis of Pure Virologic Response at Weeks 24 and 48**

The number and proportion of subjects with PVR at Weeks 24 and 48 will be summarized overall and by Parts 1 and 2. Two-sided 95% CIs will be constructed for the overall estimate of PVR using the normal approximation and the exact method.

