  - 1) Discontinuation of study drug prior to or in the analysis window due to AE or death and the last available on-treatment HIV-1 RNA < 50 copies/mL, or
  - 2) Discontinuation of study drug prior to or in the analysis window due to reasons other than AE, death, or lack of efficacy and the last available on-treatment HIV-1 RNA < 50 copies/mL, or
  - 3) Missing data during the window but on study drug.

Virologic outcomes for the US FDA-defined snapshot algorithm will also be listed.

*Note:* For switch study populations, the US FDA-defined snapshot algorithm classifies subjects who discontinue study drug due to AE or death and have the last available on-treatment HIV-1 RNA value  $\geq 50$  copies/mL as HIV-1 RNA value  $\geq 50$  copies/mL. For a treatment naïve study population, the US FDA-defined snapshot algorithm classifies these subjects as having No Virologic Data in the analysis window.

The number and percentage of subjects achieving HIV-1 RNA  $< 50$  copies/mL, HIV-1 RNA  $\geq 50$  copies/mL, and reasons for no virologic data at Weeks 12, 24, and 48 will be summarized overall and by Parts 1 and 2. Two-sided 95% CIs will be constructed for overall estimates using the exact method.

6.2.2.4. Analysis of proportion of subjects with HIV-1 RNA  $< 20$  copies/mL at Weeks 12, 24, and 48 as determined by the US FDA-defined snapshot algorithm

The number and percentage of subjects achieving HIV-1 RNA  $< 20$  copies/mL, HIV-1 RNA  $\geq 20$  copies/mL, and reasons for no virologic data at Weeks 12, 24, and 48 will be summarized overall and by Parts 1 and 2. Two-sided 95% CIs will be constructed for the overall estimate of the proportion of subjects with HIV-1 RNA  $< 20$  copies/mL using the exact method.

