6.2.2.5. Analysis of Proportion of Subjects with HIV-1 RNA  $< 50$  copies/mL  
(Missing Excluded and Missing Failure Approaches)

The proportion of subjects with HIV-1 RNA  $< 50$  copies/mL will also be analyzed using the following 2 methods for imputing missing HIV-1 RNA values, where the proportions will be expressed as percentages in all tables, listings, and figures:

- Missing Failure (M F)

In this approach, all missing data will be treated as HIV-1 RNA  $\geq 50$  copies/mL. The denominator for percentages at a visit is based on the number of subjects in the FAS.

- Missing Excluded (M E)

In this approach, all missing data will be excluded in the computation of the proportions (ie, missing data points will be excluded from both the numerator and denominator). The denominator for percentages at a visit is based on the number of subjects in the FAS with non-missing HIV-1 RNA value at that visit.

For both M F and M E analyses, the number and percentage of subjects with HIV-1 RNA in the following categories will be summarized:

- $< 50$  copies/mL
- $< 20$  copies/mL
  - $< 20$  copies/mL Not Detectable
  - $< 20$  copies/mL Detectable

- 20 to < 50 copies/mL
- $\geq 50$  copies/mL
- Missing (only applicable for M F analysis)

The proportion of subjects with HIV-1 RNA < 50 copies/mL as defined by the 2 different missing data imputation methods will be summarized for each visit. Two-sided 95% CIs will be constructed using the exact method.

For M F analysis, results will be summarized and plotted for visits up to and including Week 12. For M E analysis, results will be summarized for each visit.

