### 6.3. Changes From Protocol-Specified Efficacy Analyses

For the primary efficacy endpoint, PVR at Week 12, the protocol specifies that 95% CIs will be generated using the normal approximation method, but in the SAP, both the normal approximation and the exact methods are specified.

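### The precision quoted for the cut to 64 subjects (±5.3% or lower) uses a normal approximation that fails at response rates of 95% and above; exact limits should replace it and be named primary

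*SAP*

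**What the plan says.** SAP 1.3 reports that PVR in Part 1 was 100% at the Week 12 internal DMC review, takes it as reasonable that the observed rate for the whole study will be 95% or higher, and reduces the sample from 100 to 64. It then states that "with a sample size of 64 subjects, the width of the 95% CI will be" ±5.3% or lower, and names the large-sample approximation as the method. No other precision figure is given for the reduced size.

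The interval method for PVR is set out in several places:

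- Protocol 8.4.1: "The 95% CI will be computed using normal approximation to the binomial proportions of PVR".
- SAP 6.1.3 (Week 12, primary): "Two-sided 95% CIs will be constructed for the overall estimate of PVR and PVF using the normal approximation and the exact method".
- SAP 6.2.2.1 (Weeks 24 and 48): "Two-sided 95% CIs will be constructed for the overall estimate of PVR using the normal approximation and the exact method".
- SAP 6.3 records the difference from the protocol: "but in the SAP, both the normal approximation and the exact methods are specified".

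For the snapshot outcomes (SAP 6.2.2.3), "Two-sided 95% CIs will be constructed for overall estimates using the exact method", and for the missing = failure and missing = excluded analyses (SAP 6.2.2.5), "Two-sided 95% CIs will be constructed using the exact method". The normal approximation is not used there.

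SAP 6.1.2 adds: "No formal statistical hypotheses are being tested".

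**The concern.** With no hypothesis test, the confidence interval is the only statement of uncertainty for the primary endpoint, and the sentence in SAP 1.3 is the only quantified support for the smaller sample. At an assumed rate of 95% and n = 64, only 64 × 0.05 = 3.2 failures are expected, and fewer at higher rates. The normal approximation is unreliable with so few failures. It also errs in the favourable direction, because the lower limit sits too close to the estimate, and the lower side is the one that matters for a claim of maintained suppression.

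The extreme case is a realistic one, since Part 1 has already shown 100%. If all 64 respond, the planned table will show 100–100% beside 94.4–100%, with no rule for which to quote.

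**Working it through.** **Inputs.** n = 64, observed PVR of 95% or higher, large-sample method (SAP 1.3); two-sided 95% level, z = 1.96 (SAP 6.1.3); PVR below 80% described as unacceptable (protocol synopsis).

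**1. Reproduce the plan's figures.** Wald half-width = z × √(p(1−p)/n).

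- p = 0.90, n = 100: 1.96 × √(0.90 × 0.10/100) = 5.88%, stated as 5.9%.
- p = 0.95, n = 64: 1.96 × √(0.95 × 0.05/64) = 5.34%, stated as 5.3%.

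Both agree. The second already implies an upper limit of 95 + 5.34 = 100.3%.

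**2. Attainable outcomes.** 0.95 × 64 = 60.8, so an observed rate of at least 95% means 61, 62, 63 or 64 responders.

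**3. Intervals for those outcomes.** The exact (Clopper–Pearson) limits are the 2.5% quantile of Beta(x, n−x+1) and the 97.5% quantile of Beta(x+1, n−x). For x = n the lower limit is 0.025^(1/64) = 94.4%. Wilson intervals serve as a less conservative check. All values are percentages or percentage points.

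| Responders | Estimate | Wald | Exact | Exact lower arm | Half of exact width | Wilson |
|---|---|---|---|---|---|---|
| 61/64 | 95.3 | 90.1–100.5 | 86.9–99.0 | 8.4 | 6.1 | 87.1–98.4 |
| 62/64 | 96.9 | 92.6–101.1 | 89.2–99.6 | 7.7 | 5.2 | 89.3–99.1 |
| 63/64 | 98.4 | 95.4–101.5 | 91.6–99.96 | 6.8 | 4.2 | 91.7–99.7 |
| 64/64 | 100 | 100–100 | 94.4–100 | 5.6 | 2.8 | 94.3–100 |

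Every Wald interval has either an impossible upper limit or zero width. The exact lower limit is never within 5.3 points of the estimate. The Wilson lower arms are 8.2, 7.6, 6.8 and 5.7 points, so the result does not come from the conservatism of the exact method.

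**4. Coverage.** For a true rate p, sum the Binomial(64, p) probabilities over the outcomes whose interval contains p.

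| True PVR | Wald coverage | Wald lower limit above true PVR | Exact coverage |
|---|---|---|---|
| 95% | 83% | 16% | 98.6% |
| 96% | 92% | 7% | 98.6% |
| 97% | 85% | 14% | 98.8% |
| 98% | 72% | 27% | 99.1% |
| 99% | 47% | 53% | 99.6% |

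The nominal figure for the third column is 2.5%. Nearly all the Wald non-coverage lies there. At 95%, for example, only 63/64 (lower limit 95.4%) and 64/64 have a lower limit above the true rate; together they have probability 16.4%, out of 16.8% total non-coverage.

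**5. Smaller analysis set.** SAP 3.1.2 removes from the full analysis set (FAS) subjects whose baseline regimen included Stribild or Descovy, and their number is not given. Assuming 60 to 63 remain, the exact lower limit with three failures is 86.1% (57/60) to 86.7% (60/63).

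**The case against.** The strongest reply is that the figure is correct, its method is named in the same sentence, and the exact interval is already planned beside it, so a reader of the tables will see both. That is true, and it leaves only two gaps: the sentence in 1.3 and the missing ranking.

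Second, the SAP states a width, and half of the total exact width is 5.2, 4.2 and 2.8 points at 62, 63 and 64 responders. Like for like, only 61/64 exceeds 5.3, at 6.1. This also stands. But a single ± figure tells the reader that the lower limit is at most 5.3 points down, and that is wrong in all four outcomes.

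Third, SAP 1.3 conditions on an observed rate, whereas the coverage figures are indexed by the true rate; at a true rate of 95%, only about 60% of trials would have 61 or more responders. That is a fair distinction. The coverage results are evidence against the method in general, while the interval table addresses the sentence in 1.3 directly, and it is enough without them.

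Fourth, it could be said that the ranking is implied, because Protocol 8.4.1 specifies the normal approximation and SAP 6.3 adds the exact method. If so, the weaker interval is the default for the primary endpoint, which strengthens the case for an explicit statement. It does mean that naming the exact interval primary departs from the protocol and must be recorded.

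Finally, no decision changes: the exact lower limit stays above 80% throughout, and the cut to 64 is reported as already made. This is accepted and limits the weight of the point.

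**Conclusion.** The concern holds. The ±5.3% is correct normal-approximation arithmetic applied where that approximation breaks down. Within the range SAP 1.3 itself assumes, the lower limit lies 5.6 to 8.4 points below the estimate, and the SAP does not say which of its two PVR intervals will be quoted.

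The defect is precision that is overstated on the lower side, together with an unreliable interval reported alongside a sound one. It is not a threat to the conclusion against 80%: the pooled exact lower limit is at least 86.9% with 64 subjects, and at least 86.1% with three failures if the FAS is as small as 60. These figures rest on an observed PVR of at least 95% and, for the smaller set, on an assumed number of exclusions. The point should be corrected, but it does not put the trial's reading at risk.

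**What to change.** - **SAP 6.1.3 and 6.2.2.1:** name the exact (Clopper–Pearson) interval as the primary 95% CI for PVR, in line with the snapshot and missing-data analyses. Drop the normal approximation or label it supportive.
- **SAP 1.3:** replace the ±5.3% statement with: *With 64 subjects, the exact 95% CI is 86.9–99.0% for 61 responders, 89.2–99.6% for 62, 91.6–99.96% for 63 and 94.4–100% for 64.* Recompute if the FAS is below 64.
- **SAP 6.3:** record the choice of the exact interval as primary as a departure from Protocol 8.4.1.
- **Optional:** add exact intervals by Part to the table already planned. The size of Part 2 is not stated, so its precision cannot be given now.

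The cost is SAP wording only: the exact interval is already planned and no patient numbers change. The stated precision becomes less favourable, and the exact interval is somewhat conservative (coverage 98.6% to 99.6% at true rates of 95% to 99%).

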## **2. TYPE OF PLANNED ANALYSIS**

### **2.1. Week 12 Internal Data Monitoring Committee Analysis**

An internal Data Monitoring Committee (iDMC) reviewed the progress of the study and performed interim reviews of safety and efficacy data in order to protect subject welfare.

The initial interim review was conducted after all subjects enrolled in Part 1 completed the Week 12 visit assessment or prematurely discontinued study drug.

The iDMC's role and responsibilities, including the scope of analysis to be provided to the iDMC, were provided in a mutually agreed upon charter, which defined the iDMC membership, meeting logistics, and meeting frequency.

### **2.2. Interim Analysis**

No formal interim efficacy analysis, with the possibility of early termination for efficacy or futility, is planned.

### **2.3. Final Analysis**

After all subjects (Part 1 and Part 2) have completed the study, outstanding data queries have been resolved or adjudicated as unresolvable, and the data have been cleaned and finalized, the final analysis of the data will be performed.

